3.2 STUDY ENDPOINTS

3.2.1 Primary Endpoint:

The mean change from baseline in total FACT-P score at 12 months

3.2.2 Secondary Endpoints:

A) *Quality of Life:*

- Mean change from baseline in total FACT-P score over time
- Mean change from baseline in EORTC QLQ-C30/PR25 score over time
- Mean change from baseline in SHIM score over time

B) PSA Modulation:

- Time to PSA progression. PSA progression will be defined as a rise to greater than 50% of the baseline serum PSA or rise of 2 ng/mL or more above the nadir, whichever is higher, confirmed by repeat measurement at least 2 weeks later.
- Proportion of subjects without evidence of PSA or radiographic progression during the 24-month treatment period and with recovery of serum testosterone at 24 months. Testosterone recovery will be defined as a serum testosterone > 150 ng/dL
- Proportion of subjects with a PSA less than 0.2 ng/mL after 7 months of protocol therapy

C) Metabolic and Hormonal

- Mean change from baseline in markers of insulin resistance (including body mass index, fasting glucose/insulin, and hemoglobin A1C), fasting lipid profile, and bone mineral density as measured at the femoral neck, and lumbar spine by DEXA scan over time
- For subjects randomized to the LHRHa-based treatment arms: the time to testosterone recovery to greater than 50 ng/dL (non-castrate) and > 150 ng/dL during the Off-therapy Observation Period
- The mean change from baseline in serum DHT and estradiol levels over time

D) Safety:

[figure not shown]
- Incidence and severity of adverse events.
- Abnormal findings in physical exams and laboratory tests

E) Correlative Studies

- Frequency of subjects emerging with AR^{F876L} mutation at the end of treatment and progression.
- Frequency of subjects expressing various RNA markers previously demonstrated to confer resistance ARN-509 at baseline, end of treatment, and progression

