2. GENERAL ANALYSIS DEFINITIONS

Study Day: For safety, study day will be calculated in reference to the date of first dose. Study Day 1 corresponds to the date the subject receives first dose of study drug. For efficacy analysis, Study Day will be calculated in reference to the date of randomization.

Cycle: For the purpose of the study, a treatment cycle is defined as 28 days. Subjects will begin taking study drug on Day 1 of Cycle 1. All subjects should be following a 28-day, 28-day, 35-day schedule for their monthly visit (i.e., the 1st post-Day 1 visit is scheduled for 28 days later, the 2nd post-Day 1 visit is scheduled for 28+28 days later, the 3rd post-Day 1 visit is scheduled for 28+28+35 days later, the 4th post-Day 1 visit is scheduled for 28+28+35+28 days later, etc).

Baseline Value: Unless otherwise specified, the baseline value will be defined as the closest measurement prior to or on the day of the first dose of study drug. Change from baseline will be defined as (post-baseline value – baseline value).

Treatment Duration: Treatment duration will be defined as the duration of time from the date of the first dose of study drug to the date of last dose of study drug.

Time to event: Time to event calculations will be defined as the time from randomization to the date of the event of interest. Time to event or duration of event endpoints will be based on the actual date of the event, not visit number or visit label.

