5.3.1.2 PSA Modulation

The proportion of subjects without PSA or radiographic progression and who have recovered serum testosterone to greater than 150 ng/dL at 24 months from Day 1 will be compared for subjects treated apalutamide monotherapy vs. LHRHa monotherapy and for apalutamide + LHRHa vs. LHRHa monotherapy. The proportions by treatment will be compared using the chi-square test or Fisher's exact test as appropriate and summarized using either risk ratio or risk difference and corresponding 95% confidence interval. Results will be summarized at 24 months from Day 1 with 95% confidence intervals for each treatment arm. Subjects who withdraw from the study prior to 24 months after Day 1 will not be included and this analysis will be conducted as modified intent-to-treat (mITT).

The proportion of subjects with a PSA less than 0.2 ng/mL after 7 months of protocol therapy will be analyzed using similar approaches for proportion of subjects without evidence of PSA or radiographic progression during the 24-month treatment period and with recovery of serum testosterone at 24 months.

The probability distributions by treatment group of the time to PSA progression will be estimated using the Kaplan-Meier method. Durations will be measured from Day 1 of study treatment to the first date of PSA progression. The log-rank test will be used to compare the distribution of time to PSA progression.

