5.3.1.3 Metabolic and Hormonal Parameters

The mean change from baseline for markers of insulin resistance (including fasting glucose, insulin, body mass index, and hemoglobin A1C), fasting lipid panel (including total cholesterol, LDL, HDL, and serum triglycerides), and hormone levels (including DHT and estradiol) analyzed using a similar approach as for the primary endpoint.

The mean change in bone mineral density at the femoral neck, and lumbar spine as measured by DEXA scan will be compared for apalutamide monotherapy vs. LHRHa monotherapy and apalutamide + LHRHa vs. LHRHa monotherapy using an analysis of covariance that controls for baseline values of the corresponding measurement.

The time to serum testosterone recovery to > 50 ng/dL and > 150 ng/dL after the cessation of protocol therapy at 12 months will be compared for apalutamide + LHRHa vs. LHRHa monotherapy. The probability distributions by treatment group of the time to testosterone recovery will be estimated using the Kaplan-Meier method. The log-rank test will be used to compare the distribution of time to testosterone recovery. Subjects who discontinue study drug prior to 12 months for disease progression, unacceptable toxicity, or study withdrawal, as well as subjects who continue hormonal therapy after 12 months or receive non-protocol therapy, will not be included in the analysis of this exploratory endpoint.

No adjustment for multiple comparisons will be made for the analysis of the secondary and correlative endpoints.

Table 1: Key censoring rules

Scenario	Censoring rule
Time to PSA Progression	
 Any increase in PSA to $> 50\%$ of the baseline value or an increase of ≥ 2 ng/mL above the nadir, whichever is higher, and confirmed by repeat measurement at least 2 weeks later is considered an event. Subjects who have no PSA progression at the time of analysis will be censored at the last known date of PSA assessment. Subjects without a baseline PSA or without any post baseline values will be censored at randomization date.

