Time to Serum Testosterone Recovery	
 Any testosterone value between 12 months to 24 months that is greater than 150 ng/dL (or 50 ng/dL as the case may be) is considered an event. If a subject had testosterone recovery (between 12 and 24 months) that happened after hormonal or subsequent therapy started, then the subject is censored at the hormonal or subsequent therapy start date. If a subject had testosterone recovery (between 12 and 24 months) that happened before hormonal or subsequent therapy started, then the recovery is considered as an event. Subjects who were not treated will be censored at randomization date. Subjects who do not fall under any of the above-mentioned category will be censored at the end of on-therapy period or off-therapy period (if the subject is in the off-therapy period).

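### Followed literally, the SAP starts the testosterone-recovery clock at randomization, about 52 event-free weeks before recovery can count, and its catch-all rule censors at period end instead of at the last testosterone

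*SAP*

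**What the plan says.** The general rule in SAP section 2 is that "Time to event calculations will be defined as the time from randomization to the date of the event of interest". The baseline definition in the same section allows for exceptions; this one does not.

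The protocol (3.2.2) defines the endpoint, for the two LHRHa-containing arms, as "the time to testosterone recovery to greater than 50 ng/dL (non-castrate) and > 150 ng/dL during the Off-therapy Observation Period". SAP 5.3 repeats this in substance. SAP 5.3.1.3 then says that recovery times "after the cessation of protocol therapy at 12 months will be compared for apalutamide + LHRHa vs. LHRHa monotherapy". None of these places names a start date for the clock.

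Table 1 in SAP 5.3.1.3 gives these rules for the endpoint:
- An event is "Any testosterone value between 12 months to 24 months that is greater than 150 ng/dL" (or 50 ng/dL for the lower threshold).
- On men who never started therapy: "Subjects who were not treated will be censored at randomization date".
- As the catch-all for everyone else: "Subjects who do not fall under any of the above-mentioned category will be censored at the end of on-therapy period or off-therapy period", the latter applying if the man is in the off-therapy period.

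For PSA progression, the same table censors men without an event at their last PSA assessment.

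Two passages restrict who is analysed. SAP 2.1 removes men who withdrew before 24 months from testosterone-recovery outcomes. SAP 5.3.1.3 leaves out men who stop study drug before 12 months for progression, toxicity or withdrawal, and men who continue hormonal therapy or receive non-protocol therapy.

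For PSA progression, SAP 5.3.1.2 states that "Durations will be measured from Day 1 of study treatment to the first date of PSA progression". Protocol 6.4.2.3 and 11.4.2 also use Day 1.

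**The concern.** The endpoint asks how long a man takes to recover testosterone after stopping therapy. The only explicit origin in the SAP that reaches this endpoint is randomization, about a year earlier. Table 1 reinforces that origin. Counted from the end of therapy, censoring at randomization gives a negative time and censoring at the end of the on-therapy period gives zero. A programmer working from section 2 and Table 1 would therefore count from randomization, and a reader of the results would take the medians for times since stopping.

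The catch-all raises a second question. A man whose last testosterone was taken mid-period could be carried as observed and unrecovered beyond that date.

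Recovery time matters to the intermittent-therapy rationale (protocol 1.6 and 6.4.2.3) and is likely to be compared with published recovery times.

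**Working it through.** The documents give no planned median, event count or power for this endpoint, so there is no stated figure to reproduce.

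**1. Length of the lead-in.** Visits follow a 28, 28, 35-day pattern (SAP 2), and treatment starts within 5 days of randomization (SAP 1.5.1).
- Day 1 to end of therapy: 4 × (28 + 28 + 35) = 364 days = 52.0 weeks.
- Randomization to end of therapy: 364 to 369 days.

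**2. Effect on medians.** Protocol 6.4.2.3 cites one earlier study with medians of 12.9 weeks (to low testosterone) and 16.6 weeks (to normal). These are two thresholds in one study, used here only as example values.

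| Origin | First | Second | Difference | Ratio |
|---|---|---|---|---|
| End of therapy | 12.9 wk | 16.6 wk | 3.7 wk | 16.6 / 12.9 = 1.29 |
| Randomization | 52.0 + 12.9 = 64.9 wk | 52.0 + 16.6 = 68.6 wk | 3.7 wk | 68.6 / 64.9 = 1.06 |

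The gap before Day 1 adds up to 5 / 7 = 0.7 week to each. A difference in medians survives the shift; the level and the ratio do not.

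**3. Effect on the test.** The log-rank statistic depends only on the order of times, so a constant shift leaves it unchanged. In 400 simulated trials (27 men per arm, exponential recovery with medians 12.9 and 16.6 weeks, testosterone every 2 months), adding 364 days changed z by exactly 0. A random gap of 0 to 5 days moved |z| by about 0.17 on average. This comes from breaking ties, since simulated visits fell on exact dates. The Cox hazard ratio is likewise unchanged by a constant shift.

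**4. Effect of the catch-all.** The same simulation assumed that 30% of men leave evenly over Months 12 to 24 and remain in the analysis. That share is an assumption; the documents give none. Estimated recovery by 12 months off therapy, in the arm with median 16.6 weeks:
- Censored at last testosterone: 0.89.
- Censored at own exit date: 0.89.
- Censored at nominal Month 24: 0.78.

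A direct calculation supports the last figure. If nobody is censored before Month 24, the Kaplan-Meier estimate is the crude proportion. The median is 16.6 × 7 = 116.2 days and visits are 60.83 days apart, so the chance of recovery by visit k is F(k) = 1 − 2^(−60.83k / 116.2). This gives 0, 0.304, 0.516, 0.663, 0.766 and 0.837 for k = 0 to 5 (mean 0.514), and F(6) = 0.887. The proportion is 0.7 × 0.887 + 0.3 × 0.514 = 0.775, in line with 0.78.

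**5. Table 1 against the exclusions.** SAP 5.3.1.3 already leaves out men who stop before 12 months for the listed reasons, and SAP 2.1 leaves out withdrawals before 24 months. Table 1 still has rules for untreated men and for censoring at the end of the on-therapy period. It also has a rule for men who start hormonal or subsequent therapy, although 5.3.1.3 leaves out men who receive non-protocol therapy. The two sets of rules describe different populations.

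**The case against.** The case on the other side has five parts.

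- **Specific text may override general text.** SAP 5.3.1.3 speaks of recovery after cessation at 12 months, which can be read as setting the origin. That stands as a possible reading, so the 12-month inclusion is not settled fact. But the sentence names no start date, and Table 1 fits randomization better.
- **The impossible times may never arise.** Most men who would get zero or negative times are already excluded. This largely stands: those bullets are mainly redundant. They still contradict the exclusions and point a programmer to the wrong origin.
- **The exclusions limit the catch-all problem.** SAP 2.1 removes withdrawals before 24 months, and the wording of the catch-all leans towards each man's own period. This stands in large part. However, SAP 2.1 does not say whether men removed for progression count as withdrawn, and the end of the period is not defined.
- **The endpoint is exploratory.** SAP 5.3.1.3 calls it so. This stands and limits the weight of the point.
- **The published medians are only loosely comparable.** They follow 6 months of therapy and use a 212 ng/dL boundary. This stands; they only illustrate the shift.

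A reader might infer that the SAP counts every time-to-event endpoint from randomization. It does not: SAP 5.3.1.2 starts PSA progression at Day 1. Nor does it follow that PSA progression should move to randomization. The protocol uses Day 1, baseline PSA is the Day 1 value (protocol 7.3), and the two origins differ by at most 5 days.

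**Conclusion.** The SAP leaves the origin for time to testosterone recovery in conflict with the endpoint. Under the literal rule, the medians and the Kaplan-Meier axis carry about 52 weeks (364 to 369 days) in which no event can count.

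A reader might conclude that the comparison between arms is invalid. The documents do not support that. With most early stoppers excluded, the shift is nearly the same for every man, and the log-rank test and hazard ratio are essentially unaffected. What suffers is the reported time. SAP section 5 plans medians with confidence intervals, and it falls back on medians alone if proportional hazards fails.

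A reader might also take the fall from 0.89 to 0.78 as the expected bias from the catch-all. It is not. It needs three things together: the end of the period means nominal Month 24, about 30% of men leave early, and those men are not removed by SAP 2.1 or 5.3.1.3. If the rule means each man's own exit, the estimate did not change in the check.

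The point is worth correcting before analysis, but it concerns a secondary endpoint that the SAP calls exploratory and does not touch the primary analysis.

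**What to change.** - In SAP 2 or 5.3.1.3, state that time to testosterone recovery starts at the end of the On-therapy Period (Month 12), among men who reach it.
- In Table 1, replace the catch-all for this endpoint with censoring at the last testosterone assessment in the Off-therapy Observation Period.
- Delete the Table 1 rules for untreated men and for censoring at the end of the on-therapy period for this endpoint. Align the remaining rules with SAP 2.1 and 5.3.1.3, and say whether removal for progression counts as withdrawal.
- For time to PSA progression, keep Day 1 and add it to SAP 2 as an exception. Reconcile the Table 1 rule that "Subjects without a baseline PSA or without any post baseline values will be censored at randomization date" with that origin, so that these men contribute zero follow-up.

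The cost is a few lines of SAP text. No new data are needed.

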2.1 Analysis Sets

The following analysis sets will be used for this study:

Intent-to-Treat (ITT) Population: The ITT population includes all randomized subjects and will be classified according to their assigned treatment group, regardless of the actual treatment received. Subject disposition and efficacy analyses will be performed on data from the ITT population.

Safety Population: The safety population includes all subjects who received at least 1 dose of study drug as actually treated.

Modified Intent-to-Treat Population (mITT): For outcomes related to testosterone recovery, subjects who withdrew from the study prior to 24 months after day 1 will be excluded from the analysis.

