3 STUDY DESIGN

3.1 OVERALL STUDY CHARACTERISTICS

This is a Phase 2, randomized, open-label 3-arm multicenter study evaluating 12 months of treatment with an LHRHa monotherapy, ARN-509 monotherapy, or the combination in men with non-metastatic biochemically relapsed prostate cancer with rapidly increasing PSA levels after prior definitive therapy for localized prostate cancer. The two experimental arms (ARN-509 monotherapy; ARN-509 + LHRHa) will each be compared with a control arm of standard androgen deprivation (LHRHa monotherapy). Subjects will be stratified by PSADT (< 6 months vs. 6-12 months) and age (≤ 70 vs. greater than 70) and randomized with equal probability (1:1:1 ratio) from within each of the four strata to one of the 3 study arms.

There will be 2 treatment periods of 12 months each (24 months):

- (1) On-therapy Period lasting 12 months, during which time subjects receive randomly assigned protocol therapy
- (2) Off-therapy Observation Period from months 13 through 24

Subjects who develop progressive disease (either by serum PSA or radiographic progression) at any time during the 2 study periods will be removed from the study and will be treated as per individual investigator discretion. Subjects who discontinue before completion of the On-therapy Period in the absence of progressive disease will enter the Off-therapy Observation Period of the study. If subjects do not have evidence of PSA or radiographic progression at the end of 24 months, they will remain on study, enter a Follow-up Period, and be followed until PSA or radiographic progression or initiation of non-protocol therapy. Non-protocol therapy is defined as re-initiation of hormonal therapy or initiation of other anti-cancer therapy. The total study duration is 6 years from the date of first subject enrolled once the Off-therapy Observation Period has been completed. Subjects in the Follow-up Period will be discontinued at the time of the final clinical cutoff as described in Section 11.2.2.

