7.5.6 QOL

The FACT-P, EORTC QLQ-C30/QLQ-PR25, and SHIM questionnaires will be completed at the end of Month 3 and Month 12 or at the time of PSA or radiographic progression (if occurs before Month 12, every effort will be made to obtain the 12-month questionnaires for those who discontinue before 12 months).

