11.3 ANALYSIS POPULATIONS

Subject disposition, quality of life, metabolic, and PSA suppression endpoints will be assessed using data from the intent-to-treat (ITT) population. All subjects randomized into the study will be classified according to their assigned treatment group, regardless of the actual treatment received. Safety analyses will be performed using all subjects who received at least 1 dose of study drug, with treatment assignments designated according to actual study treatment.

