1.4 Sample Size Justification

The expected mean decline in FACT-P score and within group standard deviation for the control arm treated with 12 months of LHRHa monotherapy are 4-8 and 8-12 points, respectively, based on prior studies of measuring QOL using FACT-P among men treated with ADT [1, 2, 3]. A change in total FACT-P score that is clinically meaningful and impacts treatment in prior studies ranges from 5-8 points depending on cancer subtype [4]. Approximately 30 subjects will be randomized to each of the 3 treatment arms for this comparison. Accounting for a dropout/questionnaire non-completion rate of 10%, this will allow for 27 evaluable subjects per study arm. For the comparison of the mean change in FACT-P score between apalutamide monotherapy and LHRHa monotherapy, this sample size has 80% power to detect an effect size of at least 0.86, corresponding to a difference of 7.5 points in mean 12 month change in FACT-P

score between treatment groups with a common standard deviation for the change in each arm of 8.7 which is similar to the reported standard deviation for LHRHa monotherapy. This is based upon a 2-group t test, using a bi-directional level of significance of 0.025 (adjusted for 2 comparisons). To test for non-inferiority in QOL with apalutamide + LHRHa compared with LHRHa monotherapy, inferior QOL is defined as a greater than 7-point difference in mean change in FACT-P score between the treatment groups and the common standard deviation is again assumed to be 8.7. This sample size has 82% power to reject the null hypothesis of a difference in mean score and accept the alternative hypothesis of non-inferiority with an effect size of at least 0.81, using a 2-group t-test with 2-sided α of 0.025.

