5. EFFICACY

This section outlines the planned analyses of the primary, secondary, and other efficacy endpoints of the study.

Efficacy analyses will be performed in the ITT population, incorporating the randomization stratification factors. All continuous variables will be summarized using number of subjects (n), mean, standard deviation (SD), median, minimum, and maximum. Categorical variables will be summarized with count and percentage.

Time-to-event endpoints will be summarized using the Kaplan-Meier method [6] and displayed graphically where appropriate. Median event times and two-sided 95% confidence interval (CI) for each treatment group will be provided. Stratified Cox proportional-hazard models will be used to estimate the hazard ratio (HR) and its 95% CI. The stratification factors to be used in the analysis are PSADT (< 6 months vs. 6-12 months), and age at study entry (≤ 70 years vs. > 70 years).

The testing for the time-to-event endpoints will be based on the stratified log rank test; non-stratified log rank test will be performed as a sensitivity analysis, as appropriate. Multivariate Cox regression analysis, adjusting for important selected prognostic factors.

The proportional hazard assumption will be assessed graphically by plotting log (-log [estimated survival distribution function]) against log (survival time). The resulting graphs should have approximately parallel lines when the assumption holds. If the proportional hazards assumption is reasonably met, then the HR will be used as an estimate of treatment effect. If the proportional hazards assumption is violated, then the inference remains statistically valid for testing equality in survival distributions, but treatment effect will only be estimated using the median time to event in each treatment group.

Endpoints with binary outcome will be summarized by descriptive statistics (count and percentage) by the treatment group. The risk ratio or risk difference (treatment: control) will be reported along with the corresponding two-sided 95% CI. The two treatment groups will be compared by using the chi-square test; Fisher's exact test may be used if the expected counts in some of the cells are less than 5.

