5.2.1 Analytic Plan for the Primary Endpoint

Change from baseline in FACT-P total scale will be analyzed using a mixed-model for repeated measures. The model will include baseline scale, treatment, month (categorical), and treatment-by-month interaction as covariates. An unstructured variance-covariance matrix will be used to model within-subject errors, but simpler structures (eg, compound symmetry) may be used to ensure estimation convergence. Change from baseline will be estimated using least-squares means with factor levels weighted according to overall baseline sample means. Data up to 12 months will be included in the analysis and the primary time point of interest will be at 12 months. Contrasts will be set up to compare apalutamide monotherapy vs. LHRHa monotherapy and apalutamide + LHRHa vs. LHRHa monotherapy. To test for non-inferiority with respect to apalutamide + LHRHa compared with LHRHa monotherapy, inferior boundary is defined as a greater than 7-point difference in mean change in FACT-P total score. The estimated least-squares mean (+/- SE) over time will be presented using a line plot. A sensitivity analysis will be conducted by including data up to 24 months.

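### Non-inferiority on FACT-P rests on ITT alone, with no rule for scores collected after therapy stops, so off-drug recovery could favour the combination

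*SAP*

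**What the plan says.** **Population.** SAP 2.1 says "Subject disposition and efficacy analyses will be performed on data from the ITT population". SAP section 5 says "Efficacy analyses will be performed in the ITT population, incorporating the randomization stratification factors", and protocol 11.3 agrees: "Subject disposition, quality of life, metabolic, and PSA suppression endpoints will be assessed using data from the intent-to-treat (ITT) population". SAP 2.1 defines only two other sets, a safety set and a modified ITT set for testosterone-recovery outcomes. Under SAP 4.4, protocol deviations are summarised but define no analysis set.

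**Early stoppers.** Protocol 3.1: "Subjects who discontinue before completion of the On-therapy Period in the absence of progressive disease will enter the Off-therapy Observation Period". SAP 2.2 repeats this. Protocol 7.5.6 and SAP 2.2.5 add that "every effort will be made to obtain the 12-month questionnaires for those who discontinue before 12 months". Protocol 10.4 asks for a similar effort when a man stops for toxicity or progression.

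**Primary analysis.** SAP 5.2.1 fits a mixed model for repeated measures to data up to 12 months, with Month 12 as the time point of interest. For the combination against LHRHa, the "inferior boundary is defined as a greater than 7-point difference in mean change in FACT-P total score". The section does not say whether scores collected after treatment has stopped are used or set aside. Its one named sensitivity analysis extends the data to 24 months. SAP 5.1.2 plans no imputation and allows other sensitivity analyses, with censoring rules, only if warranted.

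**The concern.** Hypothesis 2 (protocol 2.2, SAP 1.3.2) is about quality of life with 12 months of combination therapy. Suppose a man stops the combination because it made him feel worse, recovers off drug, and then completes the Month-12 form. Under the plan his recovered score counts for the combination arm. The protocol itself expects time off androgen deprivation to improve quality of life (section 1.6).

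This kind of dilution is conservative for the superiority comparison. For a non-inferiority comparison it works the other way, because it can pull a true deficit back inside the margin. Nothing pre-specified would reveal it: the 24-month sensitivity analysis adds more off-drug data. According to protocol 2.2, a favourable finding would help to form the basis for larger trials of the combination.

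**Working it through.** **Inputs from the plan**
- Margin 7: "inferior QOL is defined as a greater than 7-point difference in mean change in FACT-P score between the treatment groups" (SAP 1.4).
- SD: "the common standard deviation is again assumed to be 8.7" (SAP 1.4).
- 30 randomised per arm less 10% leaves 27 evaluable (SAP 1.4).
- Two-sided 0.025 per comparison (SAP 1.4 and 5.1.1), which is one-sided 0.0125 for non-inferiority.
- Expected control decline c of 4 to 8 points (SAP 1.4).

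**Assumptions, because the documents give no figure**
- The share f of men who are off drug at Month 12 and supply a form: 10% to 30%.
- The degree of recovery: full or half.

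**The plan's own figure.** SE = 8.7 × √(2/27) = 2.368, with 52 degrees of freedom. With a true difference of 0, the noncentrality is 7/2.368 = 2.96.
- One-sided 0.025 (critical value 2.007): power 82.7%, which reproduces the stated 82%.
- One-sided 0.0125 (critical value 2.308): power 74.0%.

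The stated power therefore matches one-sided 0.025 rather than the two-sided 0.025 in the text. That is a separate matter, so both levels are shown where it helps.

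**Dilution, combination-arm stoppers return to the control mean.** Set the on-treatment deficit at exactly 7, so that any non-inferiority finding is false. A share f recovering by a fraction r leaves a Month-12 ITT deficit of 7 × (1 − r·f). The false non-inferiority rate is the upper tail beyond the critical value of a noncentral t with noncentrality (7 − deficit)/2.368.

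| f | Recovery | ITT deficit | Noncentrality | One-sided 0.0125 | One-sided 0.025 |
|---|---|---|---|---|---|
| 0 | – | 7.00 | 0 | 1.25% | 2.5% |
| 10% | half | 6.65 | 0.148 | 1.8% | 3.5% |
| 10% | full | 6.30 | 0.296 | 2.5% | 4.7% |
| 20% | full | 5.60 | 0.591 | 4.8% | 8.4% |
| 30% | full | 4.90 | 0.887 | 8.4% | 13.8% |

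**Stopping in both arms, with recovery to baseline.** If shares f1 (combination) and f0 (control) return to baseline, the ITT deficit is (1 − f1)(c + 7) − (1 − f0)c.
- Equal shares give 7(1 − f), the same as the full-recovery rows above.
- With f1 = 10% and f0 = 0, the deficit is 0.9 × 11 − 4 = 5.9 for c = 4 and 0.9 × 15 − 8 = 5.5 for c = 8. False non-inferiority is then 3.7% to 5.2% at one-sided 0.0125.
- The direction reverses only when f0/f1 exceeds (c + 7)/c, which is 11/4 = 2.75 for c = 4 and 15/8 = 1.9 for c = 8.

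**Extra variance.** Mixing recovered and unrecovered men widens the SD. Under equal stopping with recovery to baseline, at one-sided 0.0125, this lowers the rates slightly: to 2.4–2.5% at 10% and 4.1–4.4% at 20%.

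**The case against.** The case on the other side has five parts, and much of it stands.

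1. **ITT is legitimate.** It is a treatment-policy analysis, stated consistently in both documents, in a 90-man phase 2 trial. A reader might infer that ITT is the wrong primary population. The documents do not support that. The gap is the lack of a supporting analysis and of a rule for post-stopping scores.
2. **Collection is not certain.** A reader might infer that every early stopper supplies an off-drug Month-12 score. The plan promises only an effort. Men who stop without progression move to the schedule in protocol 7.2, which lists FACT-P only at Month 24 or at progression. A man with no form adds no off-drug value, and the dilution is smaller.
3. **Recovery may be partial.** Protocol 6.4.2.3 cites median times to testosterone recovery of 12.9 and 16.6 weeks in one trial, with up to 40 weeks in some men, and about 10 months in another report. Men who progress are treated at the investigator's discretion, so their later scores do not simply show recovery off drug.
4. **The stopping rates are assumed.** The plan's 10% covers dropout and non-completion and is already used to reach 27 per arm.
5. **An on-treatment set is no cure.** A reader might infer that analysing only men still on therapy at Month 12 would remove the bias. It would delete the men harmed most. As an illustration, suppose the worst-scoring 10% of the combination arm stop. In a normal distribution they average 1.755 SD below the arm mean, or 15.3 points. Deleting them lifts the arm mean by 15.3 × 0.1/0.9 = 1.7 points. Keeping them after full recovery to the control mean lifts it by 0.1 × (15.3 + 7) = 2.2 points, and after half recovery by 1.1. Both analyses lean towards non-inferiority.

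These points limit the size of the effect and shape the remedy. None supplies the missing rule or the missing supportive analysis.

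**Conclusion.** The concern holds as a gap in the analysis plan. The direction of the bias favours non-inferiority unless men stop about 1.9 to 2.75 times as often on LHRHa alone (recovery to baseline, control decline 8 to 4).

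Its size cannot be established from the documents. The increases in false non-inferiority depend on assumed stopping rates, an on-treatment deficit exactly at the margin, and actual collection of the form. They run from slight (1.25% to 1.8%, with 10% stopping and half recovery) to material (8.4%, with 30% stopping and full recovery). A reader might conclude that a non-inferiority result from this trial would be false or produced by early stoppers. The documents do not show that. They show only that the plan could not tell.

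**What to change.** - **Keep ITT as the primary analysis for both hypotheses.** Say in SAP 5.2.1 how FACT-P scores collected after discontinuation enter it.
- **Add one supportive analysis to SAP 5.2.1 for the non-inferiority contrast.** Use the same mixed model in all randomised men. Exclude only FACT-P scores collected after assigned therapy is discontinued or non-protocol therapy starts. Keep earlier on-treatment scores such as Month 3.
- **State the reading rule in advance.** Non-inferiority is described as robust only if this analysis agrees with ITT.
- **Treat men still on therapy at Month 12 as descriptive only**, with the selection bias stated.
- **Reconcile the passages on collection.** The off-therapy schedule in protocol 7.2 should be reconciled with protocol 7.5.6 and 10.4 and SAP 2.2.5 on whether the Month-12 form is obtained after early stopping.

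**Cost.** One extra model and a short paragraph. The supportive analysis assumes that the set-aside scores are missing at random given the earlier ones, and it is less precise. As a guide, if 10% of the 27 Month-12 scores per arm are set aside (about 24 left), a simple t test at one-sided 0.0125 has about 68% power, against 74% at 27.
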